1.1 Background

1.1.1 Treatment resistant depression

Depression is a serious and life-threatening condition with high rates of morbidity and a chronic disease course. It is a common illness worldwide, with more than 264 million people affected (WHO 2020). When long-lasting and with moderate or severe intensity, depression causes the affected person to suffer greatly, impairing the ability to work, self-care, and maintain relationships.

Despite a broad availability of antidepressant medication, about a third of patients suffering from MDD fail to respond fully to antidepressant treatment of adequate duration and dose, and the majority fail to maintain long-term response to standard antidepressants (Rush et al 2006). This chronicity of symptoms predisposes patients to treatment resistance.

Treatment-resistant depression (TRD) is defined as a lack of clinically meaningful improvement after treatment with at least 2 different antidepressant agents prescribed in adequate dosages for adequate durations.

Patients suffering from TRD are very likely to have suicidal ideation and experience a disproportionate burden of illness causing significant impairment and increased morbidity (Shelton et al 2010).

Therefore, there is a high unmet medical need for rapid-acting antidepressants that are either more effective or better tolerated, treatments that can effectively interrupt a depressive episode and are able to prevent future depressive episodes.

Ketamine, which is a N-methyl-D-aspartate (NMDA) receptor antagonist, has been shown to be effective in TRD in off-label research, but is limited by psychotomimetic side effects (Katalinic et al 2013, Browne and Lucki 2013). Further, ketamine has been shown to be rapid-acting and reduce suicidality (Katalinic et al 2013). The efficacy of ketamine provides the rationale for targeting N-methyl-D-aspartate (NMDA) receptor inhibition as a rapid-onset antidepressant mechanism.

SPRAVATO® (esketamine), a non-competitive NMDA receptor antagonist, is approved for the treatment of TRD and is also approved for MDD with acute suicidal ideation or behavior by the Food and Drug Administration (FDA) and for moderate to severe episode of MDD as acute short-term treatment in conjunction with an oral antidepressant for the rapid reduction of symptoms which according to clinical judgement constitute a psychiatric emergency by the European Medicines Agency (EMA]). While both ketamine and SPRAVATO have demonstrated a certain level of efficacy and showed rapid mode of action, their safety profiles are not without adverse effects meaningful both for patients and clinicians.

Targeting a specific subset of NMDA receptors is one approach to potentially mitigate adverse effects of NMDA receptor inhibition while retaining the antidepressant efficacy. Preskorn (Preskorn et al 2008) demonstrated that infusion of traxoprodil, a negative allosteric modulator selective for the NR2B subtype of NMDA receptors, also known as CP-101,606, was efficacious in TRD patients with the magnitude and duration of response comparable to those

of ketamine with low potential to produce dissociative effects in patients. Ibrahim et al (Ibrahim et al 2012) reported that MK-0657 (Rislenemdaz, a selective NR2B antagonist) did not induce dissociative effects in TRD patients and was generally safe. Taken together, this suggest that achieving safe, yet rapid-onset antidepressant efficacy is feasible with a compound selectively inhibiting NR2B receptor.

1.1.2 MIJ821 Preclinical summary

MIJ821 is a highly potent, selective and reversible low molecular weight negative allosteric modulator (NAM) targeting the NR2B sub-unit of the N-methyl-D-aspartate receptors (NMDARs).

The primary pharmacological properties of MIJ821 were characterized *in vitro* and *in vivo* and established a pharmacological basis for the intended clinical use. Non-clinical drug disposition and exposure effect were assessed. *In vivo*, MIJ821 was shown to distribute into the rat brain.

The non-clinical safety profile of MIJ821 was evaluated in rats and dogs using the intravenous (i.v.) bolus route in studies of up to 6 weeks in duration. The choice of rats and dogs as preclinical species is justified by the relevance of these species in terms of pharmacology and metabolism. Key findings were as follows:

- While MIJ821 shows some in vitro off-target activity below 1 micromolar (μM), the risk of off-target pharmacology at therapeutically relevant exposures is considered low.
- In safety pharmacology, MIJ821-related findings included cardiovascular effects (human Ether-à-go-go-Related Gene (hERG) channel potassium current inhibition half maximal inhibitory concentration (IC50) = 1.1 μ M; increased heart rate in dogs) and, in rats, lack of pinna response and increased respiration rate.
- In pivotal 6-week Good Laboratory Practice (GLP) studies, MIJ821 given i.v. twice a week was tolerated with no adverse effects and the top dose of 10 mg/kg was defined as the no observed adverse effect level (NOAEL) in rats and dogs. The main targets identified included the Central Nervous System (CNS) (clinical signs assumed to represent exaggerated pharmacological effects) and the cardiovascular system (as seen in safety pharmacology). There were no MIJ821-related local findings at the i.v. infusion or subcutaneous (s.c.) injection sites.
- MIJ821 did not induce neuronal vacuolation or necrosis.
- MIJ821 is not genotoxic or phototoxic.
- Embryo-fetal development (EFD) studies in rats and rabbits (daily i.v. administration during gestation) showed that MIJ821 is not teratogenic. In rats, MIJ821 was well tolerated. In rabbits, doses ≥ 9 mg/kg/day were above the maximal tolerated dose (MTD) for maternal animals and caused embryo lethality.
- NOAELs were identified in all pivotal studies with safety margins adequate for the pursued indication.

Further details are provided in the Investigator's Brochure (IB).

1.1.3 MIJ821 Clinical summary

The MIJ821 clinical development program aims to evaluate MIJ821 as a short-term, fast-acting treatment for adult participants with MDD who have acute suicidal ideation and behavior (initial indication) and as a treatment of adult participants with TRD (follow-on indication).

MIJ821 has been studied in a Phase 1 First-In-Human study (FIH, CMIJ821X2101) in healthy volunteers (HV) and in a Phase 2a Proof-of-Concept (PoC CMIJ821X2201) clinical study in participants with TRD after i.v. administration. A Phase 1 study is also ongoing to investigate the safety, tolerability and pharmacokinetic (PK) of subcutaneous MIJ821 in HVs (CMIJ821A02101).

First-In-Human study (CMIJ821X2101)

In a FIH study, MIJ821 was intravenously administered at single ascending doses (SAD) of 0.016, 0.048, 0.16, 0.24, 0.32, and 0.48 mg/kg (Part 1) and at repeated doses of 0.32 mg/kg given one week apart (Part 2) to HVs. Dissociative AEs, amnesia and sedation were observed at doses higher than 0.16 mg/kg.

In term of pharmacokinetics, no obvious PK difference has been identified between the two dosing events in the repeated dose part of the study.

PoC study in TRD participants (CMIJ821X2201)

This PoC study evaluated the safety and efficacy responses to MIJ821 in participants suffering from TRD (defined as failing two or more prior antidepressants, one in the current episode) assessed by the MADRS, a validated and widely employed method in depression trials (see details in Section 8.3.1). Participants were randomized with a ratio of 3:3:3:3:6:4 to one of six treatment arms: i) MIJ821 0.16 mg/kg one infusion per week (weekly), ii) MIJ821 0.16 mg/kg one infusion every other week (biweekly), iii) MIJ821 0.32 mg/kg weekly, iv) MIJ821 0.32 mg/kg biweekly, v) placebo weekly, and vi) ketamine 0.5 mg/kg weekly.

A total of 72 participants were randomized: 41 on MIJ821 across the 4 MIJ821 arms, 11 on ketamine and 20 on placebo. Out of these 72 participants randomized, 70 received study drug and were included in both efficacy and safety analyses. Two participants were randomized but did not receive study drug: 1 patient in MIJ821 0.32 mg/kg biweekly arm for physician decision and 1 patient in ketamine arm for adverse event before treatment. Overall, 53 (75.7%) completed the treatment and 50 (71.4%) completed the follow-up period. The most common reason for treatment discontinuation was participant/guardian decision (15.7%).

The primary endpoint of the study was the change from baseline in the total MADRS score at 24 hours after the start of the infusion compared to placebo. Both the MIJ821 0.16 mg/kg and the 0.32 mg/kg doses (pooled across weekly and bi-weekly dosing regimens) were superior to placebo on the primary endpoint. The MADRS adjusted arithmetic mean difference vs. placebo was -8.25 points (p=0.0013) for the pooled 0.16 mg/kg group and -5.71 points (p=0.0196) for the pooled 0.32 mg/kg group.

The safety and tolerability profile of MIJ821 was generally favorable across all the dosing regimens. The overall incidence of AEs was similar across the MIJ821 dose groups (61.9% for pooled 0.16 mg/kg and 68.4% for pooled 0.32 mg/kg) and the ketamine group (60.0%), which

were all higher than in the placebo group (35.0%). The most commonly reported AEs were amnesia (overall incidence across treatment groups: 14.3%), dizziness (14.3%), somnolence (11.4%), feeling abnormal (8.6%), headache (8.6%), depersonalization/derealization disorder (7.1%), fatigue (7.1%), dry mouth (5.7%) and nausea (5.7%).

Phase 1 study in HVs with s.c. MIJ821 (CMIJ821A02101)

This is a SAD study with randomized, participant and investigator blinded, placebo controlled design to investigate the safety, tolerability and PK of s.c. administered MIJ821 in healthy participants. The study is ongoing and will include approximately 32 non-Japanese and 12 Japanese participants. Study participants (non-Japanese) have already been enrolled into three sequential cohorts and received a single s.c. dose of 1, 4 or 12 mg MIJ821 or placebo. Eight participants completed treatment in each cohort with a randomization ratio 3:1 for MIJ821 to placebo. Subsequently, 12 Japanese participants will be enrolled into a single cohort and receive a dose of s.c. MIJ821 or placebo. The exact dose of MIJ821 in the Japanese cohort will be determined based on the results of the cohorts with non-Japanese participants.

Preliminary blinded data with s.c. MIJ821 are available from the ongoing double blind, placebo controlled SAD study (CMIJ821A02101). In this study, dissociative AEs were reported in the 4 and 12 mg cohorts, where MIJ821 exposure was comparable to that reached by 0.048 and 0.16 mg/kg i.v. doses in the FIH study, respectively. All of these events were mild or moderate in severity and resolved without treatment.

1.2 Purpose

The main purpose of this non-confirmatory study is to evaluate the safety and efficacy of a single s.c. MIJ821 injection in addition to standard pharmacological antidepressant (SoC) treatment in participants suffering from TRD assessed by the MADRS (Montgomery and Asberg 1979), a validated and widely employed scale in depression trials, evaluated 24h after study drug administration.

Furthermore, it is expected that this study will provide information about the dose-response and exposure-response relationship of the antidepressant effect of MIJ821 after single s.c. injection, which will be used to guide dose selection for confirmatory studies.

2 Objectives, endpoints and estimands

Table 2-1 Objectives and related endpoints

Objective(s)	Endpoint(s)	
Primary objective(s)	Endpoint(s) for primary objective(s)	
• To assess efficacy of MIJ821 (versus placebo) in treatment resistant depression after single s.c. injection	MADRS total score at 24 hours after s.c. injection compared to baseline assessment	
Secondary objective(s)	Endpoint(s) for secondary objective(s)	
To assess safety and tolerability of MIJ821 after single s.c. injection	 Incidence and severity of treatment-emergent adverse events (TEAEs), including AEs of special interest; standard safety assessments such as vital signs, ECG, hematology, blood chemistry, urinalysis; Clinician-Administered Dissociative States Scale 	

Objective(s) Endpoint(s) (CADSS) score, Modified Observer's Assessment of Alertness/Sedation (MOAA/S), C-SSRS, memory assessment using orientation questions, results of local tolerability assessments • PK properties of MIJ821 in plasma described by • To assess MIJ821 PK in plasma after single s.c. injection Area under the curve from time zero to time of last measurable concentration (AUClast), maximum plasma drug concentration (Cmax), time to reach maximum plasma concentration (Tmax) (parameters not limited). • To assess the duration of antidepressant effect of • MADRS total score at Day 8, 15, 22 and 29 visits MIJ821 compared to baseline • To characterize the dose-response and exposure-• Dose-response relationship of MIJ821 with respect response relationship of MIJ821 to change from baseline in MADRS total score at 24 hours after single s.c. injection • Exposure-response relationship of MIJ821 with respect to change from baseline in MADRS total score at 24 hours (Day 2)

2.1 Primary estimands

The primary clinical question of interest is: What is the effect of s.c. MIJ821 (versus placebo) given in addition to standard pharmacological antidepressant (SoC) treatment 24 hours after the injection of the study drug on change in depressive symptoms in participants with TRD, who have already failed to adequately respond to at least two conventional antidepressants.

Rationale

The justification for the primary estimand is that it will allow to estimate the rapid effect of the study drug in a population of depressed participants, who are considered treatment resistant, based on the definition above. A rapid response is clinically valuable as conventional antidepressants might need several weeks to achieve reduction of depressive symptoms.

The primary estimand is described by the following attributes:

- 1. Population: participants with treatment resistant depression, who have failed to show adequate treatment response to at least 2 antidepressants previously.
- 2. Primary variable: change from baseline to 24 hours post dose in the MADRS total score.
- 3. Treatment of interest: the randomized treatment (the investigational treatment MIJ821 or the placebo treatment) administered as a single s.c. injection on Day 1. The dose of the allowed concomitant medication (i.e., SoC) for depression must remain stable during the trial.
- 4. Handling of intercurrent events (IEs) prior to MADRS assessment at 24 hours (for more details see Section 12.4.3):
 - New intake or change in concomitant medications/therapies which have a potential confounding effect: hypothetical strategy
 - Intake of prohibited medications: hypothetical strategy
 - Intake of rescue medications: hypothetical strategy
 - IEs related to pandemic: hypothetical strategy
 - IEs leading to study discontinuation due to adverse (AEs), lack of efficacy or other reasons: treatment policy

Participants who took prohibited medications, rescue medications, or took new or change concomitant therapy which have potential confounding effect, will continue in the study and be assessed as scheduled.

Further details about the concomitant therapy, prohibited and rescue medications are provided in Section 6.2.

The summary measure: difference in variable means between study drug and placebo.

[figure not shown]
The Multiple Comparisons Procedures - Modeling (MCP-Mod) approach will be used to assess the primary objective (for more details on this approach see Section 12.4.2).

2.2 Secondary estimands

Not applicable

3 Study design

Figure 3-1 Study Design

This is a non-confirmatory, randomized, double-blind, placebo-controlled, parallel-group trial in participants with TRD to evaluate the efficacy, safety, tolerability and pharmacokinetics of single subcutaneous MIJ821 administration in addition to pharmacological antidepressant SoC treatment. Approximately 56 participants will be randomized in a total of 20-25 centers worldwide.

Participants will be randomly allocated to one of the following four treatment arms in a 1:1:1:1 ratio:

- Single administration of MIJ821 s.c. 10 mg
- Single administration of MIJ821 s.c. 4 mg
- Single administration of MIJ821 s.c. 1 mg
- Single administration of Placebo s.c.

The screening period starts when the participant signs the informed consent form and can last up to 28 days. The eligibility of participants is determined based on the assessments performed during the screening period and also on Day 1, prior to randomization. With the exception of lab results, all other baseline evaluations including the primary efficacy scale (MADRS) must be performed on Day 1, prior to randomization, and reviewed against the eligibility criteria before dosing. On Day 1, eligible participants will then be randomized to one of the above treatment arms.

Treatment is administered as a single s.c. injection on Day 1, followed by a safety observation at the clinical site for a minimum of 4 hours after administration. Study participants will be continuously observed by site personnel during the first 30 minutes after administration for emergence of adverse events, particularly CNS or cardiovascular AEs. Safety assessments will

include physical examinations (PEs), ECGs, vital signs, standard clinical laboratory evaluations (hematology, blood chemistry, and urinalysis), administration of the CADSS, MOAA/S, C-SSRS, and memory assessment using orientation questions. Local tolerability will be evaluated by visual inspection of the injection area. Injection site abnormalities reaching the threshold of mild changes will also be assessed quantitatively (refer to Section 8.5.4).

Participants will be allowed to leave the clinical site at the earliest 4 hours after dosing, if all of the following criteria are fulfilled:

- The participant does neither report nor present with any CNS adverse events (dissociation, amnesia, sedation)
- There is no increase in suicidal intensity or new occurrence of suicidal ideation as assessed by C-SSRS
- No clinically relevant QTcF prolongation (QTcF≥500 msec or increase in QTcF from baseline≥60 msec)
- No clinically relevant abnormalities in blood pressure (BP) (90≤Sysotlic BP (SBP) ≥180 mmHg or 50≤Diastolic BP (DBP) ≥105 mmHg or increase or decrease in SBP of at least 20 mmHg or increase or decrease in DBP of at least 15 mmHg from baseline) or any increase in BP that is accompanied by symptoms, such as headache, dizziness, nausea, visual disturbances or other neurological symptoms
- The investigator does not identify any other AEs that require continued monitoring

If the participant cannot be released from the clinical site 4 hours after dosing, extended safety monitoring will be performed as described below.

The post-dose follow-up period will continue for 4 weeks (28 days) after treatment. On-site visits to assess efficacy and safety are scheduled on Day 2 (24 hours post-dose) and subsequently every week (i.e., on Days 8, 15, 22 and 29) during the follow-up period. The assessment to address the primary objective will be performed at Day 2 (24 hours post-dose). Phone calls will be conducted 3 days after each on-site visit with the exception of End-of-study (EOS) visit. The EOS visit will be completed on site on Day 29. The total duration of the study is approximately 8 weeks (56 days), including screening.

Extended safety monitoring in case of AEs on Day 1 (4 hours after dosing)

If extended monitoring is required beyond the minimum 4 hours of monitoring on Day 1, the following will be assessed:

- Monitoring of CNS adverse events (dissociation, amnesia, sedation):
 - If there are any dissociative AEs, amnesia or somnolence/sedation present, the participant should be monitored at the clinical site until these AEs are fully resolved. If the dissociative AEs or cognitive symptoms do not resolve within 6 hours after onset, the participant will be required to stay at the clinical site for overnight monitoring and can be discharged after the assessments are completed on Day 2 and the AEs have resolved. The onset and resolution time of dissociative and cognitive AEs should be captured as accurately as possible. The following assessments are recommended to follow CNS AEs, whenever possible (e.g., participant is awake):

- If dissociative AEs are present, it is recommended to administer the CADSS every hour until the total score returns to baseline or normal level (i.e., total score not higher than 4)
- If memory gaps/amnesia is present, it should be assessed with orientation questions at least once per hour until the amnesia is resolved
- Sedation/somnolence should be assessed by questioning or the administration of the MOAA/S every hour until the AE is resolved
- Monitoring of suicidal ideation or behavior:
 - If moderate to severe suicidal ideation or any suicidal behavior is present, either based on rating scales or investigator judgment, the investigator must hospitalize the participant at least overnight
 - If suicidal ideation is mild, either based on rating scales or investigator judgment, the investigator's judgment can be used to allow the participant to leave the clinical setting, but in that case arrangements should be made such that family members or friends are present with the participant for at least 24 hours. If such arrangements cannot be made, it is recommended that the participant is hospitalized at least overnight
- Monitoring of QTcF prolongation:
 - If the initial QTcF prolongation is confirmed by repeated ECG at least 10 minutes later, close observation of the participant should be initiated at the investigator's discretion
 - ECG should be performed every 30 minutes until QTcF is below 500 msec and the increase from baseline is less than 60 msec
 - Serum electrolyte levels should be determined and corrected, if needed (in particular hypokalemia, hypomagnesemia)
 - Consultation with a cardiologist can be performed at the investigator's discretion
- Monitoring of increased blood pressure:
 - Increase in blood pressure should be monitored but initial treatment is not recommended unless clinically indicated. Blood pressure increase associated with MIJ821 treatment is usually transient and the blood pressure typically returns to predose values within 3-4 hours
 - At 1.5 hours post-dose, if SBP is ≥160 mmHg and/or the DBP ≥100 mmHg, assessments should continue every 30 minutes until:
 - 1. The blood pressure is <160 mmHg SBP and <100 mmHG DBP, or
 - 2. As per investigator's clinical judgment, the participant is clinically stable, or
 - 3. The participant is referred for appropriate medical care, if clinically indicated
 - 4. If the blood pressure remains ≥ 160 mmHg SBP and/or / ≥100 mmHg DBP after 4 hours post-dose, the participant should be referred for immediate medical treatment

4 Rationale

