 - Long QT syndrome, family history of idiopathic sudden death or congenital long QT syndrome
 - Concomitant medication(s) with a "Known Risk of TdP" that cannot be discontinued or replaced by safe alternative medication
- 15. Participant has mean systolic blood pressure > 140 mmHg or diastolic blood pressure > 90 mmHg at Screening or pre first dose on Day 1; or past history of hypertensive crisis.
- 16. History of hemorrhagic stroke or known cerebrovascular disorders (e.g. aneurysm or arteriovenous malformation) or known aneurysmal vascular disease in other location (e.g. aorta).
- 17. Pregnancy (including a positive human chorionic gonadotropin [hCG] test) or lactation at screening or baseline.
- 18. Women of child-bearing potential, defined as all women physiologically capable of becoming pregnant, unless they are using highly effective methods of contraception

during dosing and for 1 week after stopping of investigational drug. *Highly effective contraception methods include:*

- Total abstinence from heterosexual intercourse (when this is in line with the preferred and usual lifestyle of the subject). Periodic abstinence (e.g. calendar, ovulation, symptothermal, post-ovulation methods) and withdrawal are not acceptable methods of contraception.
- Female sterilization (have had surgical bilateral oophorectomy with or without hysterectomy), total hysterectomy or tubal ligation at least six weeks before taking investigational drug. In case of oophorectomy alone, only when the reproductive status of the woman has been confirmed by follow up hormone level assessment.
- Male sterilization (at least 6 months prior to screening). For female participants on the study the vasectomized male partner should be the sole partner for that participant.
- Use of intrauterine device (IUD) or intrauterine system (IUS). In case of use of an IUD or IUS, the device or system should have been placed and well tolerated by the patient for a minimum of 3 months before taking the study treatment.

Use of oral (estrogen and progesterone), injected or implanted hormonal methods of contraception other forms of hormonal contraception are not allowed for the purpose of contraception.

If local regulations deviate from the contraception methods listed above and require more extensive measures to prevent pregnancy, local regulations apply and will be described in the ICF.

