10.2.3 Cardiac Monitoring

To ensure participant safety cardiac monitoring has to be followed for all participants.

Please refer to Section 16.4 and Table 16-1 for clinically notable vital signs and ECG alert threshold values.

Post dose cardiac monitoring:

Every clinically significant cardiac event should be followed up by the investigator or designated personnel at the trial site, as summarized below.

- If the initial abnormality is confirmed, close observation of the participant can be initiated based on investigator's discretion
- Causality assessment of the cardiac event should be evaluated
- Thorough follow-up of the cardiac event. These investigations can include based on investigator's discretion: increasing the cardiac monitoring level; initiating additional diagnostic or therapeutic procedures to ensure patient safety, and to better characterize the finding and/or its cause; consultancy with a cardiologist
- Hospitalization of the participant if appropriate

Post dose QT prolongation:

In case of a clinically significant postdose QT prolongation, in addition to the abovementioned cardiac monitoring measures, the following additional measures are recommended

• Determine the serum electrolyte levels (in particular hypokalemia, hypomagnesemia). If abnormal, correct abnormalities before resuming study treatment.

Post dose blood pressure monitoring:

The following monitoring criteria based on post-dose blood pressure assessments during the dosing phase should be followed:

At 1.5 hours post-dose, if the SBP is \geq 160 mmHg and/or the DBP \geq 100 mmHg, assessments should continue every 30 minutes until:

- The blood pressure is <160 mmHg SBP and <100 mmHg DBP, or
- In the investigator's clinical judgment, the subject is clinically stable or
- The subject is referred for appropriate medical care, if clinically indicated
- If the blood pressure remains ≥ 160 mmHg SBP and/or / ≥100 mmHg DBP, 4 hours after dosing, the subject should be referred for immediate medical treatment.

For participants with SBP \geq 180 mmHg but <200 mmHg and/or the DBP is \geq 110 mmHg but <120 mmHg participant should be referred to a cardiologist, or other specialist for a follow-up assessment.

All follow-up information and procedures performed must be recorded as appropriate in the CRF.

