16.1 Appendix 1: Clinically notable laboratory values and vital signs

Table 16-1 16-1 Clinically notable values for vital signs

Variable	Criterion value	Change relative to baseline
Heart rate/pulse	≥120 bpm; ≤50 bpm	increase of ≥ 15 bpm decrease of ≥ 15 bpm
Systolic blood pressure	≥180 mm Hg; ≤90 mm Hg	increase of ≥ 20 mm Hg decrease of ≥ 20 mm Hg
Diastolic blood pressure	≥105 mm Hg; ≤50 mm Hg	increase of ≥ 15 mm Hg decrease of ≥ 15 mm Hg
bpm= beats per minute		

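### The blood-pressure rule for leaving the site is malformed, so its low limits do nothing, and its diastolic limit (105 mmHg) is looser than the 4-hour referral limit (100 mmHg)

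*Protocol*

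**What the plan says.** **Release rule (Protocol Section 3).** Participants may leave at 4 hours at the earliest, if every listed criterion is met. The blood-pressure criterion treats these as abnormal:
- "90≤Sysotlic BP (SBP) ≥180 mmHg or 50≤Diastolic BP (DBP) ≥105 mmHg"
- a change from baseline, in either direction, of at least 20 mmHg systolic or 15 mmHg diastolic
- any rise accompanied by symptoms

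A further criterion is that "The investigator does not identify any other AEs that require continued monitoring".

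**Route to extended monitoring (Section 3).** "If the participant cannot be released from the clinical site 4 hours after dosing, extended safety monitoring will be performed as described below".

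**Referral rule.** In Section 3 it is the last item under monitoring of increased blood pressure, within extended monitoring. If pressure remains ≥160 mmHg systolic and/or "≥100 mmHg DBP after 4 hours post-dose, the participant should be referred for immediate medical treatment". Section 10.2.3 gives the same limits without tying them to extended monitoring: "≥100 mmHg DBP, 4 hours after dosing, the subject should be referred for immediate medical treatment".

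**Clinically notable values (Table 16-1).** Systolic "≥180 mm Hg; ≤90 mm Hg"; diastolic "≥105 mm Hg; ≤50 mm Hg". SAP Table 5-3 has the same limits.

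**Baseline cap (Section 5.2, exclusion 15).** Excluded if "mean systolic blood pressure > 140 mmHg or diastolic blood pressure > 90 mmHg at Screening or pre first dose on Day 1". No lower blood-pressure limit is set for entry.

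**The concern.** There are two separate faults in one safety criterion.

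First, the inequality signs are wrong. Any systolic value of 180 or more already exceeds 90, and any diastolic value of 105 or more already exceeds 50, so neither low limit can exclude anyone. Low readings are then caught only by the change limits. The fault also reaches beyond discharge: Table 8-2 points sites to Sections 5.2 and 3 for the notable blood-pressure values that need a repeat measurement, and Section 5.2 gives only upper limits.

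Second, the release and referral rules use different diastolic limits at the same time point. In Section 3 the referral rule sits in a part of the text that the reader is sent to only when release has been refused. A participant who passes the release criterion is not led to it there, although Section 10.2.3 applies it regardless.

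Raised blood pressure is an adverse event of special interest (Section 10.2.5). At the Cmax of 0.16 mg/kg i.v., Table 4-1 reports mean placebo-adjusted diastolic rises of 10.7 and 16.4 mmHg in two studies. The 10 mg s.c. dose has a simulated mean Cmax 18% lower (Section 4.2.1). A rise of 10–14 mmHg is therefore of the size the drug has produced at peak, although the rule is applied at 4 hours, when the effect is expected to have declined.

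**Working it through.** There is no planned figure to reproduce; the check is of logic. Write b for baseline and v for the 4-hour reading, both in whole mmHg.

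**Inputs**
- Release barred as written: SBP if (90 ≤ v and v ≥ 180) or |v − b| ≥ 20; DBP if (50 ≤ v and v ≥ 105) or |v − b| ≥ 15 (Section 3)
- Referral: SBP v ≥ 160 or DBP v ≥ 100 (Sections 3 and 10.2.3)
- Baseline: SBP b ≤ 140, DBP b ≤ 90 (exclusion 15)
- No symptoms, since a symptomatic rise bars release anyway

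**Step 1: the literal reading.** (90 ≤ v and v ≥ 180) is the same as v ≥ 180, and (50 ≤ v and v ≥ 105) is the same as v ≥ 105, for every v.

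**Step 2: systolic, high side.** With b ≤ 140 and v ≥ 160, the rise is at least 160 − 140 = 20, which bars release. Conflicting pairs: **0**.

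**Step 3: diastolic, high side.** A conflict needs 100 ≤ v ≤ 104 and v − b ≤ 14. The second condition gives b ≥ 100 − 14 = 86; the cap gives b ≤ 90.

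| Baseline DBP | 4-hour DBP that passes release but is ≥100 | Pairs |
|---|---|---|
| 86 | 100 | 1 |
| 87 | 100–101 | 2 |
| 88 | 100–102 | 3 |
| 89 | 100–103 | 4 |
| 90 | 100–104 | 5 |
| Total | | **15** |

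**Step 4: low side, literal reading, baseline above the limit.**
- SBP: v ≤ 90 with a fall under 20 needs b from 91 to 109. For b = 90 + k there are 20 − k values of v; summed over k = 1 to 19 this is **190** pairs (for example 105 to 88, a fall of 17).
- DBP: v ≤ 50 with a fall under 15 needs b from 51 to 64. For b = 50 + k there are 15 − k values; summed over k = 1 to 14 this is **105** pairs.

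**Step 5: effect of the correction**

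| Rule | Diastolic conflict pairs | Low SBP pairs missed | Low DBP pairs missed |
|---|---|---|---|
| As written | 15 | 190 | 105 |
| Inequalities corrected only | 15 | 0 | 0 |
| Corrected, plus DBP ≥100 bars release | 0 | 0 | 0 |

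The counts show where the rules disagree, not how often participants would fall there.

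**The case against.** The best case for leaving the text alone has five parts.

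- **The meaning is recoverable.** Table 16-1 gives the same four numbers correctly, Section 10.2.3 refers to that table, and the literal reading makes 90 and 50 pointless. Site staff would probably read it as intended. This stands, and it makes the low-side fault a drafting error with an obvious correction. The 190 and 105 pairs exist only on the literal reading.
- **The rules can be applied together.** Section 3 permits release rather than ordering it, and Section 10.2.3 applies the referral rule to everyone. A careful site could satisfy both. But the release list is meant to say who may go, and it passes a reading that another section sends for immediate treatment.
- **The rule says pressure remains high.** It follows a check at 1.5 hours, so a first reading of 100 at 4 hours may not trigger it. The 15 pairs are therefore an upper bound. A sustained reading of 100–104 still falls in the gap, and that is the more worrying case.
- **Monitoring may already be under way.** A participant at ≥100 at 1.5 hours is on 30-minute checks under Section 10.2.3. However, those checks may end on a judgment that the participant is clinically stable.
- **Other safeguards exist.** The investigator can hold a participant for another adverse event, and Section 10.2.5 asks for on-site follow-up of events of special interest until resolution or absence of safety risk. These lower the risk but rest on judgment; they do not reconcile two numeric limits.

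**Conclusion.** Both faults hold. As printed, the low limits have no effect. The diastolic release limit is looser than the referral limit for symptom-free participants with baseline DBP 86–90 and 4-hour DBP 100–104: 15 whole-number pairs, against none for systolic pressure. This assumes that the baseline used for the change limits meets exclusion 15 and that an earlier reading was also high enough for the pressure to count as remaining raised.

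The documents give no frequency. Section 4.1.3 expects blood-pressure effects to decline over the first 4 hours, and the study has about 56 participants given a single dose, so few are likely to be affected. Power, type I error and the planned analyses do not change. The point should be fixed because the error is in an operative safety threshold and the correction is simple.

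**What to change.** In Section 3, replace the absolute limits with: SBP ≤90 or ≥180 mmHg, or DBP ≤50 or ≥105 mmHg. Add as a bar to release: SBP ≥160 or DBP ≥100 mmHg at 4 hours. The systolic half of that addition is redundant under the present baseline cap, but it keeps the release and referral rules in the same terms.

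The sponsor's medical lead should also state how ≤90 and ≤50 apply to a participant whose baseline is already at or below them. Otherwise that participant could not be released even with no change.

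The cost is a wording change in Section 3 and a notice to sites. Section 14.1 requires a written amendment with the usual approvals, so the change could be carried in the next one, or implemented at once if the sponsor judges it necessary for participant safety. Blood pressure is already measured at 4 hours, so no procedure or visit is added. A few participants may stay longer than 4 hours.
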